### **Randomization:**

The patients were randomized assigned into two groups. The samples were allocated into two groups by a simple randomization technique using computer generated random numbers. The

choice of procedure was determined based on whether the number fell into either group A or B. Group A had wound closure via polypropylene suture while Group B with polyglactin 910.

### **Statistical analysis:**

Data analysis was performed using SPSS version 24.0. After assessing the normality of the data, all continuous variables were represented as medians (IQR). Discrete variables are shown as frequencies and percentages. The Hollander score prediction model was used to evaluate the correlation between the Hollander score and all independent variables. Statistical significance was set at  $P < 0.05$ .

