## **MATERIALS AND METHODS:**

The present parallel randomized controlled trial was conducted to compare the outcomes of wound closure using polypropylene versus subcuticular polyglactin 910 sutures in patients undergoing total knee arthroplasty (TKA).

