### **Patient selection:**

All patients aged 50-80 years, belonging to either sex, diagnosed with end-stage osteoarthritis or post-traumatic arthritis, and scheduled for bilateral primary total knee arthroplasty at the Department of Orthopedics, Indus Hospital and Health Network, Karachi were enrolled in the study. Exclusion criteria included patients having existing skin, neuromuscular, or connective tissue disorders, rheumatoid arthritis, immunosuppression, morbid obesity, and pregnancy. All patients provided voluntary informed written consent before enrolment in the study.

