### **Intervention:**

In all patients undergoing primary TKA, one knee was closed using polypropylene, whereas the other was closed with Polyglactin 910 sutures. All surgeries were performed by the same surgical team using a standard medial parapatellar approach. The number of sutures and wound closure techniques were standardized across both groups.

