### **Results:**

A total of forty patients were enrolled in this study. There was a female predominance in the present study, with a M:F ratio of 1:2.07 (Table 1). The median (IQR) age of the study participants was 58 years (50.5 - 69.0 years). Hypertension was the most frequent comorbidity [33(82.5 %)], followed by diabetes mellitus [15 (37.5%)].

At baseline, ASA of Anesthesiologists grade II was the most frequently observed class in the study cohort (85%). The complications and the Hollander score of the patients as observed in the two suture groups are displayed in Table 2. Presentation of erythema was observed in more patients in the polypropylene group versus polyglactin 910 group for postoperative days 3, and 7 i.e. 21 versus 16, and 14 versus 12 respectively but then became vice versa for days 15, and 30 during which the polyglactin 910 group had more patients i.e. 5 versus 3 and 2 versus 0 respectively. The polyglactin 910 group had a higher number of patients in comparison to the polypropylene group for parameters such as wound dehiscence (3 versus 0), wound discharge (24 versus 16), blisters (3 versus 2), stitch abscess (3 versus 1),  $>1$  cm of cellulitis (16 versus 12), step-off border (17 versus 15),  $>2$ mm width scar (10 versus 9), and suture removal due to infection (3 versus 1). The polyglactin 910 group also had a higher of patients with systemic symptoms compared to the polypropylene group (7 versus 4). Poor overall cosmesis was observed in an equal number of patients in both suture groups i.e. 8 (20%). The median Hollander score in both suture groups was reported to be 6. In terms of the correlation coefficient, age [-0.076 (0.042)], weight [-0.121 (0.047)], and presence of diabetes mellitus [-

1.335 (0.741)] had a positive while height [0.095 (0.045)] had a negative correlation on the prediction of Hollander score

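### Each patient had one knee closed with each suture, but the stated methods name no suture comparison and do not say how two knees from one patient are handled

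*Combined protocol and SAP*

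**What the plan says.** The aim and design label come in Materials and Methods: "The present parallel randomized controlled trial was conducted to compare the outcomes of wound closure". Patient selection restricts entry to patients "scheduled for bilateral primary total knee arthroplasty", and Intervention states: "In all patients undergoing primary TKA, one knee was closed using polypropylene, whereas the other was closed with Polyglactin 910 sutures".

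Randomization describes the allocated unit in two ways: "The patients were randomized assigned into two groups", and then "The samples were allocated into two groups by a simple randomization technique using computer generated random numbers". Group A is polypropylene and group B is polyglactin 910. The section does not say how the random number fixed the suture for the left or the right knee.

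Statistical analysis gives medians with interquartile ranges for continuous variables, counts and percentages for discrete ones, a threshold of P < 0.05, and one model: "The Hollander score prediction model was used to evaluate the correlation between the Hollander score and all independent variables". It names no test or estimate that compares the sutures and no term for the patient. The Results text gives counts and a median Hollander score per suture (6 in both), and model coefficients for age, weight, height and diabetes. It shows no suture difference, confidence interval or P value. Table 2 is cited but is not in the text available.

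**The concern.** The trial exists to compare two sutures. With one knee per suture in each patient, that comparison is a within-patient difference, and its precision depends on how alike the two knees are. The stated analysis leaves this open. Someone working from it would have either no suture comparison at all or one whose handling of the pairing they must guess.

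The guess can matter. When the knees of a patient are positively correlated, an unpaired analysis overstates the standard error of the difference. For a binary outcome, the marginal counts alone do not determine the paired result: the discordant pairs are needed, and the visible text does not give them.

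**Working it through.** **Is the design really paired?** Results states: "A total of forty patients were enrolled in this study". Poor cosmesis is 8 (20%) under each suture, so the denominator is 8 / 0.20 = 40 per suture, equal to the number of patients. Separate patient groups are also impossible. Discharge on polyglactin 910 needs at least 24 patients and day-3 erythema on polypropylene at least 21, and 24 + 21 = 45 > 40. The counts agree with Intervention and not with a parallel split.

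**No plan figure to reproduce.** The document gives no sample-size calculation, effect size or suture P value. The figures below are therefore new. They assume two-sided tests, since sidedness is not stated.

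**Discharge, 24/40 versus 16/40, difference 0.20.**

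- *Unpaired.* Chi-square without correction = 80 × (24×24 − 16×16)² / (40×40×40×40) = 80 × 320² / 40⁴ = 3.2, P = 0.074. Fisher exact P = 0.117.
- *Paired.* Let a be the number of patients with discharge in both knees (0 to 16). The discordant counts are b = 24 − a and c = 16 − a, and 40 − a − b − c = a have it in neither. Exact McNemar P is the two-sided binomial P for b of b + c at 0.5.
- *Paired Newcombe interval, without continuity correction of phi.* phi = (a² − bc) / √(24×16×16×24) = (40a − 384) / 384, which is zero at a = 9.6. The Wilson limits are 0.446 to 0.737 for 24/40 and 0.263 to 0.554 for 16/40. The lower limit is then 0.20 − 0.154 × √(2(1 − phi)), and the upper limit is 0.20 + 0.137 × √(2(1 − phi)). Setting phi = 0 gives the unpaired interval, −0.018 to 0.393.

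| a (both knees) | b v c | phi | Exact McNemar P | Paired 95% CI |
|---|---|---|---|---|
| 0 | 24 v 16 | −1.00 | 0.268 | −0.108 to 0.473 |
| 10 | 14 v 6 | 0.04 | 0.115 | −0.013 to 0.389 |
| 11 | 13 v 5 | 0.15 | 0.096 | −0.001 to 0.378 |
| 12 | 12 v 4 | 0.25 | 0.077 | 0.011 to 0.367 |
| 13 | 11 v 3 | 0.35 | 0.057 | 0.025 to 0.355 |
| 14 | 10 v 2 | 0.46 | 0.039 | 0.040 to 0.342 |
| 16 | 8 v 0 | 0.67 | 0.0078 | 0.074 to 0.311 |

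The exact test falls below 0.05 from a = 14, and the Newcombe interval excludes zero from a = 12. At 12 and 13 the two disagree.

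**How far this reaches.** For a count difference d, the smallest possible exact McNemar P is 2 × 0.5^d, reached when all discordant pairs go one way. P < 0.05 needs d ≥ 6. Among the 14 binary comparisons visible in Results, discharge has d = 8. Next come day-3 erythema, d = 5 (0.0625), cellulitis, d = 4 (0.125), and dehiscence and systemic symptoms, d = 3 (0.25). The rest have d ≤ 2. Only discharge can fall below 0.05 in the exact test.

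**Hollander score, illustrative only.** No spread or within-patient correlation is given, so take normal theory and assumed intraclass correlations. The unpaired 95% half-width is t(78) × √(2/40) = 0.445 SD. The paired half-width, t(39) × √(2(1 − ICC)/40), is 0.378, 0.320 and 0.248 SD at ICC 0.3, 0.5 and 0.7.

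**The case against.** A reader might infer from the parallel wording that an unpaired test was planned or run. The document does not support that. No test of the sutures is named, and someone following Intervention would pair. An unpaired test is one possible reading, no more.

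A reader might also infer that patients rather than knees were randomised. The text does not settle this, because *samples* could mean knees. Nor can one say that suture was left out of the model or that no comparison was made. Suture may be among the independent variables, and Table 2 may hold a test. The four coefficients shown in Results are all patient-level, but that does not prove suture was excluded. These points limit the finding to the stated methods. They do not supply a stated contrast.

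The discharge example has limits of its own. It is the largest of 14 visible differences, no primary outcome is named and nothing is adjusted for multiplicity, so it does not show that a real suture effect was missed. Its threshold also depends on the method: mid-P McNemar gives 0.049 at a = 12 and 0.035 at a = 13, and 0.031 for day-3 erythema at maximum overlap. All of that stands. It is a reason to fix the method and say which result governs, not a reason to leave the method unstated.

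For the Hollander score, harm is not shown. The medians are equal, and the half-widths rest on assumed correlations and on normal theory that a rank-based analysis would not use.

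**Conclusion.** The point holds for the stated methods. The design is 40 within-patient pairs, established by Patient selection and Intervention and confirmed by the counts. The design label contradicts it, the randomised unit is ambiguous, and no suture contrast or handling of two knees per patient is stated. As written, the analysis does not answer the trial's question.

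The demonstrated size is modest. For discharge, the visible margins are compatible with exact paired P values from 0.268 to 0.0078, or from 0.115 to 0.0078 if the knees are positively correlated (a ≥ 10), against 0.074 unpaired. No other visible binary outcome can cross 0.05 in the exact test. This assumes 40 complete pairs and two-sided testing, and it is an illustration rather than evidence of a suture effect. What the unseen Table 2 contains, and what was actually run, remain unknown. The text should be corrected and the paired results reported.

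**What to change.** Results already exist, so label all of this post hoc.

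1. Reconcile Materials and Methods and Randomization with Intervention. State the knee as the unit, the patient as the pair, and how the suture for each knee was chosen. If that was not random, say so and limit the conclusion: a paired test does not repair it.
2. Report the within-patient difference in Hollander score with a 95% confidence interval, by one paired method fixed before the re-run. Wilcoxon signed-rank with a Hodges-Lehmann interval suits the median reporting; a model with a patient random effect is an alternative if ties are heavy. State the visit.
3. For each binary knee-level outcome, report the discordant-pair counts, exact McNemar P and a paired Newcombe 95% interval. State in advance which governs if they disagree, and note that there is no multiplicity adjustment. Report systemic symptoms (7 versus 4) per patient unless the text explains how they were assigned to a knee.
4. If the prediction model is kept, include suture as a term and cluster on patient.

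The cost is retrieving the knee-allocation record, revising three sections and re-running existing data with the two knees linked by patient. No new patients are needed. The downside is that the re-analysis is post hoc and some results may become less favourable.

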### **Results:**

A total of forty patients were enrolled in this study. There was a female predominance in the present study, with a M:F ratio of 1:2.07 (Table 1). The median (IQR) age of the study participants was 58 years (50.5 - 69.0 years). Hypertension was the most frequent comorbidity [33(82.5 %)], followed by diabetes mellitus [15 (37.5%)].

At baseline, ASA of Anesthesiologists grade II was the most frequently observed class in the study cohort (85%). The complications and the Hollander score of the patients as observed in the two suture groups are displayed in Table 2. Presentation of erythema was observed in more patients in the polypropylene group versus polyglactin 910 group for postoperative days 3, and 7 i.e. 21 versus 16, and 14 versus 12 respectively but then became vice versa for days 15, and 30 during which the polyglactin 910 group had more patients i.e. 5 versus 3 and 2 versus 0 respectively. The polyglactin 910 group had a higher number of patients in comparison to the polypropylene group for parameters such as wound dehiscence (3 versus 0), wound discharge (24 versus 16), blisters (3 versus 2), stitch abscess (3 versus 1),  $>1$  cm of cellulitis (16 versus 12), step-off border (17 versus 15),  $>2$ mm width scar (10 versus 9), and suture removal due to infection (3 versus 1). The polyglactin 910 group also had a higher of patients with systemic symptoms compared to the polypropylene group (7 versus 4). Poor overall cosmesis was observed in an equal number of patients in both suture groups i.e. 8 (20%). The median Hollander score in both suture groups was reported to be 6. In terms of the correlation coefficient, age [-0.076 (0.042)], weight [-0.121 (0.047)], and presence of diabetes mellitus [-

1.335 (0.741)] had a positive while height [0.095 (0.045)] had a negative correlation on the prediction of Hollander score

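### The Hollander score is compared between sutures only by two equal group medians, with no within-patient comparison, although each patient had one knee closed with each suture

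*Combined protocol and SAP*

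**What the plan says.** Under Statistical analysis, "all continuous variables were represented as medians (IQR"), and the only analysis named for this score is a regression-type one: "The Hollander score prediction model was used to evaluate the correlation between the Hollander score and all independent variables". No test between sutures is named, paired or unpaired.

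The Intervention section sets up a within-patient design: "one knee was closed using polypropylene, whereas the other was closed with Polyglactin 910 sutures". The Results state "A total of forty patients were enrolled in this study" and then "The median Hollander score in both suture groups was reported to be 6". They also give three counts that bear on cosmetic appearance, polyglactin 910 first:

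- border: "step-off border (17 versus 15"
- scar: "mm width scar (10 versus 9"
- overall appearance: "Poor overall cosmesis was observed in an equal number of patients in both suture groups i.e. 8 (20" per cent of each group)

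The Results refer to Table 2 for the score by suture; that table is not in the available text. Nowhere do the documents state the score's range, direction, items or day of scoring. The Outcomes section lists four assessment days (3, 7, 15 and 30), and the three counts above carry no day.

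**The concern.** With one knee per suture in each patient, the cosmetic question is how the two knees of the same patient differ. Two group medians do not answer it. A median of 40 values depends only on the 20th and 21st in order, so many knees can change score without moving it. If 6 is also the top of the scale, the median is at its least sensitive, because every departure lies on one side of it.

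At stake is how the result is read. Two equal medians invite the conclusion that the sutures give the same cosmetic result, when the text holds no estimate, interval or test to support that. The prediction model uses the same score, so any doubt about how the score was built carries over to it.

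**Working it through.** **Denominator.** There are 40 patients and one knee per suture, so 40 knees per suture. The stated percentage agrees: 8/40 = 20%. The medians themselves cannot be recomputed without knee-level data, so I bound what they allow.

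**Assumption for all that follows.** The score runs 0 to 6, 6 is best, and it has six one-point items, three of which are step-off border, wide scar and poor overall appearance. The documents do not say this. On a 0 to 6 scale that counts defects and includes appearance, the reverse direction does not fit: a median of 6 would need the 20th to 40th values, 21 knees, all with poor appearance, and only 8 are reported. On a scale extending beyond 6, the ceiling argument and the bounds below do not apply.

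**Room below the median.** A median of 6 at the ceiling needs the 20th and 21st ordered values both to be 6, so at most 19 knees score below 6.

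**How little the median constrains the score.** As an illustration only, not a reconstruction of this trial, compare 39 sixes and one 5 with 21 sixes, ten 4s and nine 3s. Both have median 6. The totals are 239 and 193, a mean difference of 46/40 = 1.15 points, and an unpaired Mann-Whitney test gives p = 0.000003.

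**What the reported counts leave open.**

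- The three counted items cost polyglactin 910 (17 + 10 + 8)/40 = 35/40 = 0.875 points per knee, and polypropylene (15 + 9 + 8)/40 = 32/40 = 0.80. On these items alone the mean difference is 0.075 points.
- Three further items could each fall on up to 19 knees: at most 3 × 19/40 = 1.425 points per group.
- Polypropylene mean minus polyglactin mean therefore lies between 0.075 − 1.425 = −1.35 and 0.075 + 1.425 = +1.50 points. These are limits, not expectations.
- The number of knees below 6 is tightly bounded: 17 to 19 for polyglactin 910 and 15 to 19 for polypropylene. The largest gap is 19 − 15 = 4 knees. Even if all four were discordant in one direction with none in the other, an exact McNemar test gives p = 2 × 0.5⁴ = 0.125.

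**Do the counts fit a median of 6?** The number of knees with at least one of the three defects must be 19 or fewer.

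| | Polyglactin 910 | Polypropylene |
|---|---|---|
| Possible range | 17 to 35 | 15 to 32 |
| Expected if independent | 40 × (1 − 23/40 × 30/40 × 32/40) = 26.2 | 40 × (1 − 25/40 × 31/40 × 32/40) = 24.5 |
| Chance of 19 or fewer if independent (counts fixed) | 0.000015 | 0.001 |
| Scar and appearance marks that must fall on already marked knees | 35 − 19 = 16 of 18 | 32 − 19 = 13 of 17 |
| If every poor-appearance knee has another listed defect: wide scars needed on step-off knees | 17 + 10 − 19 = 8 of 10 | 15 + 9 − 19 = 5 of 9 |
| Same overlap expected by chance | 17 × 10/40 = 4.25 (P = 0.008) | 15 × 9/40 = 3.4 (P = 0.19) |

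Independence is only a benchmark. In a latent-normal model with equal correlation among the three defects, the expected number of affected knees falls to 19.6 for polyglactin 910 at a correlation of 0.7, and to 20.0 for polypropylene at 0.5 (18.0 at 0.7). The required overlap is therefore strong in one group and moderate in the other. Any further item in the score would tighten both.

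**The case against.** The scale is not in the documents, so everything about a ceiling is conditional. That stands, and a reader should not take it as documented that 6 is the best possible score.

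Table 2 is not available and the plan calls for interquartile ranges. On the assumed scale at least 17 and 15 of 40 knees score below 6, so the lower quartile is below 6 in both groups and a reported range would show it. That also stands, so it cannot be said that the trial reported no spread. A spread by group is still not a within-patient comparison, and the methods name none. The prediction model may have included suture as a variable, but the Results give coefficients only for age, weight, diabetes and height.

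A reader might infer that the median contradicts the defect counts. The documents do not support that. A median of 6 is feasible in both groups, overall appearance would naturally go with the other defects, and the counts and the score may come from different days.

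A reader might also infer that the score cannot show a difference, or that a real difference is being hidden. The first is true of the median, not of the score. For the second, the three reported items differ by only 0.075 points per knee on average.

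Finally, the Results never state that cosmesis was equal, and they list the item counts beside the medians. That is correct; the point concerns the missing comparison, not a false claim.

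**Conclusion.** The point holds in this form: the available text compares the Hollander score between sutures only through two equal medians, and the methods name no within-patient comparison although the design provides one. This does not depend on the scale, because equal group medians neither estimate nor test a paired difference.

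If the score has six one-point items with 6 best, up to 19 of 40 knees per suture can lie below the median unseen by it, and the mean difference is confined only to −1.35 to +1.50 points. On the same assumption the median needs strong overlap of defects for polyglactin 910 and moderate overlap for polypropylene. That justifies a data check and shows no error. The direction of the score cannot be recovered from the model either, since the Results describe negative coefficients as positive correlations and a positive one as negative.

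**What to change.** In the Statistical analysis section, add a within-patient comparison of the Hollander score at one stated visit: for example a Wilcoxon signed-rank test, with the paired difference and its 95% confidence interval. If many differences are zero, the mean paired difference with a bootstrap interval will say more than the median difference. A count of knees below 6 can be shown, but should not carry the comparison, given the four-knee bound above. Because results are already reported, label the analysis as added afterwards.

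In the Results, report that comparison with the full score distribution by suture. State the score's range, direction, items and scoring day. Check each knee's score against its recorded items at the same visit, and rerun the prediction model if they disagree. Do not present equal medians as evidence of equal cosmesis.

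The cost is some re-tabulation of data already held, and a cosmetic result that looks less clean than two identical medians.

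### Results names diabetes and age as correlates of the Hollander score without applying the P < 0.05 rule; diabetes misses it however the unlabelled brackets are read, age only if they are standard errors

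*Combined protocol and SAP*

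**What the plan says.** The Statistical analysis section of the combined protocol and SAP describes one modelling step: "The Hollander score prediction model was used to evaluate the correlation between the Hollander score and all independent variables". It then gives one decision rule: "Statistical significance was set at" P < 0.05. It does not state the type of model, the covariates, whether the unit is the patient or the knee, or whether tests are one- or two-sided.

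The Results section reports the model in one sentence. It opens "In terms of the correlation coefficient, age [-0.076 (0.042)], weight [-0.121 (0.047)], and presence of diabetes mellitus" and closes, after a page break that separates the minus sign from the diabetes figure, with "1.335 (0.741)] had a positive while height [0.095 (0.045)] had a negative correlation on the prediction of Hollander score". Each factor has a number followed by a second number in brackets. The second number is not identified, and nothing separates factors that meet the rule from those that do not.

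On the amount of data, Results states: "A total of forty patients were enrolled in this study". The Intervention section puts one suture type on each knee of the same patient, and Results gives a Hollander score for each suture group.

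**The concern.** The document sets a significance threshold, and the Hollander model is the only analysis it names that could be judged against it. When the model is reported, the threshold is not used. Four factors are singled out of all independent variables; sex, hypertension and ASA class are described elsewhere in Results but do not appear in that sentence. A reader will naturally take the four as the factors that the model found to matter.

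At stake is the trial's only statement on what is associated with wound appearance. Diabetes is recorded in 15 of the 40 patients. If its figures do not meet the stated rule, listing it beside weight without qualification lends it support that the analysis has not shown. The same question arises for age, with an answer that depends on what the brackets contain.

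A second issue concerns precision. Age, weight, height and diabetes take one value per patient, but each patient has two knee scores. If the 80 scores were entered as independent rows, the standard errors for these factors are too small.

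**Working it through.** **Inputs.** All come from Results except the rule (Statistical analysis).
- Age -0.076 (0.042); weight -0.121 (0.047); diabetes -1.335 (0.741); height 0.095 (0.045).
- 40 patients. Poor cosmesis in 8 (20%) of each suture group implies 8/0.20 = 40 knees per group, 80 in all.
- Diabetes 15/40 = 37.5%. Age interquartile range 50.5 to 69.0.
- Rule P < 0.05, taken as two-sided (assumption).

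The document gives no labelled P value or test statistic for the model, so there is no such figure to reproduce. The percentages do reproduce: 33/40 = 82.5%, 15/40 = 37.5%, 8/40 = 20%. A value of -1.335 lies outside -1 to 1, so these are regression coefficients rather than correlations.

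**Reading A: the bracket is a standard error.** Ratio = |coefficient| / SE. Two-sided P runs from the normal distribution to t with 30 df, a range that covers 40 patients or 80 knees.

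| Factor | Ratio | Two-sided P | Meets P < 0.05 |
|---|---|---|---|
| Age | 0.076/0.042 = 1.81 | 0.070 to 0.080 | No |
| Diabetes | 1.335/0.741 = 1.80 | 0.072 to 0.082 | No |
| Weight | 0.121/0.047 = 2.57 | 0.010 to 0.015 | Yes |
| Height | 0.095/0.045 = 2.11 | 0.035 to 0.043 | Yes |

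95% CI as coefficient ± 1.96 × SE:
- Diabetes: -1.335 ± 1.452, that is -2.79 to 0.12.
- Age: -0.076 ± 0.082, that is -0.158 to 0.006.

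Rounding does not rescue age: the largest ratio it allows is 0.0765/0.0415 = 1.84, P = 0.065. The sign of a coefficient does not affect any of these P values.

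**Reading B: the bracket is a P value.** Age 0.042, weight 0.047 and height 0.045 pass. Diabetes, at 0.741, does not.

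**Which reading fits better.** For one model, SE × SD(covariate) × √n should give roughly the same residual SD for each factor, apart from collinearity. The SD of diabetes is √(0.375 × 0.625) = 0.484. The SD of age is (69.0 - 50.5)/1.349 = 13.7, with 8 as a low alternative (assumption). With n = 40:
- Reading A: age 0.042 × 13.7 × 6.32 = 3.6 (2.1 with SD 8); diabetes 0.741 × 0.484 × 6.32 = 2.3. These agree.
- Reading B: the P values imply an SE of 0.076/2.11 = 0.036 for age and 1.335/0.333 = 4.0 for diabetes (t with 35 df). The residual SDs become 1.8 to 3.1 and about 12. Reconciling them needs a variance inflation for diabetes 15 to 45 times that of age.

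Standard errors are therefore the more coherent reading, though the document does not confirm it.

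**Two knees per patient (conditional).** If 80 knees were entered as independent rows under reading A, the SE of a patient-level factor should be multiplied by √(1 + rho), where rho is the within-patient correlation (not given; 0.1 to 0.5 assumed). With t on 35 df:
- Height: 2.11/√1.1 = 2.01, P about 0.05; 2.11/√1.3 = 1.85, P about 0.07; 2.11/√1.5 = 1.72, P about 0.09.
- Weight: 2.57/√1.5 = 2.10, P about 0.04.

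If one score per patient was used, none of this applies.

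**The case against.** The strongest reply is that Results reports the direction of four coefficients and claims nothing more. It does not call any factor significant, established or prognostic, and a significance threshold does not restrict which coefficients may be described. This stands as to wording: the fault is leaving the rule unapplied and the figures unlabelled, not a false claim of significance.

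Three further points also stand.
- A reader might infer that two of the four factors are unsupported. The document does not establish that. Its brackets are unlabelled, and if they are P values age passes, leaving one of four. Nor is P of 0.07 to 0.08 with 40 patients evidence of no association; it is inconclusive.
- Sidedness is not stated. One-sided, under the standard-error reading, age and diabetes would come to about 0.035 to 0.041. Nothing in the document specifies a directional test, so two-sided is the ordinary assumption, but it remains an assumption.
- A reader might also infer that height falls once the two knees are allowed for. That needs an 80-row fit and a value of rho, and the document gives neither.

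Finally, the trial's purpose is to compare two sutures, and this model does not bear on that comparison. That limits the point's reach. It does not remove it, because for diabetes the answer is the same on both readings.

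**Conclusion.** The point holds in a limited form. With two-sided testing, diabetes does not meet the document's own rule whichever way its bracket is read, yet it is listed without distinction beside factors that do. Age fails to meet the rule only on the standard-error reading, which is the better supported by the printed figures but is not certain. Weight meets the rule on both readings; so does height on the figures as printed.

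The proper description of diabetes, and of age if the brackets are standard errors, is inconclusive. The two-knee issue is a gap in what is stated rather than a demonstrated error: its size is known only under assumptions. The sentence also calls the negative coefficients positive and the positive one negative. That needs correcting separately and plays no part in this conclusion.

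**What to change.** In Results:
1. State what the bracketed figure is, and call the leading figures regression coefficients.
2. Give the coefficient, 95% CI and P for every factor in the model, including those not now named. Do not drop factors because they miss the threshold.
3. Say that diabetes, and age if the brackets are standard errors, did not meet P < 0.05 and is inconclusive.

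In Statistical analysis:
1. State the model type, the covariates, that tests are two-sided (if they were), and whether the unit is the patient or the knee.
2. If 80 knee scores were entered as independent rows, refit with a patient random intercept and report those intervals. This keeps suture type in the model, which averaging the two knees would not.

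The cost is some rewording and at most one refit on data already held. One or two predictor statements will be softened, and the intervals may widen.
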